10.2. Study Oversight

10.2.1. Data Quality Assurance

All patient data relating to the study will be recorded in a printed or electronic CRF unless transmitted to the sponsor or designee electronically (e.g., laboratory data). The investigator is responsible for verifying that data entries are accurate and correct by physically or electronically signing the CRF.

The investigator must maintain accurate documentation (source data) that supports the information entered in the CRF.

The investigator must permit study-related monitoring, audits, IRB review, and regulatory agency inspections and provide direct access to source data documents.

The sponsor or designee is responsible for the data management of this study including quality checking of the data.

Study monitors will perform ongoing source data verification to confirm that data entered into the CRF by authorized site personnel are accurate, complete, and verifiable from source documents; that the safety and rights of patients are being protected; and that the study is being conducted in accordance with the currently approved protocol and any other study agreements, ICH GCP, and all applicable regulatory requirements.

10.2.2. Source Documents

Source documents provide evidence for the existence of the patient and substantiate the integrity of the data collected. Source documents are filed at the investigator's site.

Data reported on the CRF that are transcribed from source documents must be consistent with the source documents or the discrepancies must be explained. The investigator may need to request previous medical records or transfer records, depending on the study. Also, current medical records must be available.

Definitions of what constitutes source data can be found in the Study Procedures Manual.

10.2.3. Study and Site Closure

The sponsor designee reserves the right to close the study site or terminate the study at any time for any reason at the sole discretion of the sponsor. Study sites will be closed on a rolling basis upon database lock for each site individually or as the Sponsor determines.

A study site is considered closed when all required documents, study supplies, and investigational product have been collected and/or destroyed, and a study-site closure visit has been performed.

The investigator may initiate study-site closure at any time, provided there is reasonable cause and sufficient notice is given in advance of the intended termination.

Reasons for the early closure of a study site by the sponsor or investigator may include but are not limited to:

- Failure of the investigator to comply with the protocol, the requirements of the IRB or local health authorities, the sponsor's procedures, or GCP guidelines
- Inadequate recruitment of patients by the investigator
- Discontinuation of further CPX-POM development

10.2.4. Reporting of Results and Publications

CicloMed will fulfill its commitment to publicly disclose the results of this study through posting the results on the www.clinicaltrials.gov web site.

A clinical study report will be prepared and provided to the regulatory agency(ies). CicloMed will ensure that the report meets the standards set out in the ICH Guideline for Structure and Content of Clinical Study Reports (ICH E3). Note that an abbreviated report may be prepared in certain cases.

Any investigator will submit any proposed publication or presentation along with the respective scientific journal or presentation forum at least 30 days before submission of the publication or presentation. The investigator will comply with CicloMed's request to delete references to its confidential information (other than the study results) in any paper or presentation and agrees to withhold publication or presentation for an additional 60 days in order to obtain patent protection if deemed necessary.

The results of this study may be published or presented at scientific meetings. If this is foreseen, the investigator agrees to submit all manuscripts or abstracts to the sponsor before submission. This allows the sponsor to protect proprietary information and to provide comments.

The sponsor will comply with the requirements for publication of study results. In accordance with standard editorial and ethical practice, the sponsor will generally support publication of multicenter studies only in their entirety and not as individual site data. In this case, a coordinating investigator will be designated by mutual agreement.

Authorship will be determined by mutual agreement and in line with International Committee of Medical Journal Editors authorship requirements.

10.2.5. Study Files and Retention of Records

The investigator must maintain adequate and accurate records to enable the conduct of the study to be fully documented and the study data to be subsequently verified. These documents should be classified into at least the following two categories: (1) investigator's study file, and (2) patient clinical source documents.

The investigator's study file will contain the protocol/amendments, CRF and query forms, IRB, and governmental approval with correspondence, informed consent, drug records, staff curriculum vitae and authorization forms, and other appropriate documents and correspondence.

The required source data includes at least the following information for each patient:

- patient identification (name, date of birth, gender);
- documentation that patient meets eligibility criteria, i.e., history, physical examination, and confirmation of diagnosis (to support inclusion and exclusion criteria);
- participation in trial (including trial number);
- trial discussed and date of informed consent;
- dates of all visits;
- documentation that protocol specific procedures were performed;
- results of efficacy parameters, as required by the protocol;
- start and end date (including dose regimen) of trial medication;
- record of all AEs and other safety parameters (start and end date, and preferably including causality and intensity);
- concomitant medication (including start and end date, dose if relevant; dose changes should be motivated);
- date of trial completion and reason for early discontinuation, if applicable.

All clinical study documents must be retained by the investigator until at least 2 years after the last approval of a marketing application in an ICH region (i.e., United States, Europe, or Japan) and until there are no pending or contemplated marketing applications in an ICH region; or, if no application is filed or if the application is not approved for such indication, until 2 years after the investigation is discontinued and regulatory authorities have been notified. Investigators may be required to retain documents longer if required by applicable regulatory requirements, by local regulations, or by an agreement with CicloMed. The investigator must notify CicloMed before destroying any clinical study records.

Should the investigator wish to assign the study records to another party or move them to another location, CicloMed must be notified in advance (i.e. in the case of a Principal

Investigator moving to a new location, retiring, etc.). If a study site is assigned to another investigator for archival oversight or if the files are to be moved, this change will be noted in a memo, the Sponsor will be contacted, and the IRB will be notified depending on the IRB requirements.

If the investigator cannot guarantee this archiving requirement at the study site for any or all of the documents, special arrangements must be made between the investigator and CicloMed to store these in sealed containers outside of the site so that they can be returned sealed to the investigator in case of a regulatory audit. When source documents are required for the continued care of the patient, appropriate copies should be made for storage outside of the site.

Biological samples at the conclusion of this study may be retained in storage by the sponsor for a period up to 2 years for purposes of this study.

10.2.6. Case Report Forms

For each patient enrolled, a CRF must be completed and signed by the Principal Investigator or sub-investigator (as appropriate) within a reasonable time period after data collection. This also applies to records for those patients who fail to complete the study (even during a screening period if a CRF was initiated). If a patient withdraws from the study, the reason must be noted on the CRF. If a patient is withdrawn from the study because of a treatment-limiting AE, thorough efforts should be made to clearly document the outcome.

10.2.7. Inspections

The investigator should understand that source documents for this trial should be made available to appropriately qualified personnel from CicloMed or its representatives, to IRBs, or to regulatory authority or health authority inspectors.

10.2.8. Protocol Compliance

The investigator is responsible for ensuring the study is conducted in accordance with the procedures and evaluations described in this protocol.

10.2.9. Study Discontinuation

Both the sponsor and the investigator reserve the right to terminate the study at any time. Should this be necessary, both parties will arrange discontinuation procedures and notify the appropriate regulatory authority(ies) and IRBs. In terminating the study, CicloMed and the investigator will assure that adequate consideration is given to the protection of the patients' interests.

## LIST OF ABBREVIATIONS

AE	Adverse Event
ATC	Anatomical Therapeutic Chemical
BMI	Body Mass Index
BSA	Body Surface Area
ChIP	Chromatin Immunoprecipitation
CI	Confidence Interval
CRF	Case Report Form
CTCAE	Common Terminology Criteria for Adverse Events
CS	Clinically Significant
CSR	Clinical Study Report
CTCAE	Common Terminology Criteria for Adverse Events
CV	Coefficient of Variation
DNA	Deoxyribonucleic Acid
ECG	Electrocardiogram
ECOG	Eastern Cooperative Oncology Group
ICH	International Conference on Harmonization
IQR	Interquartile Range
IV	Intravenous
MedDRA	Medical Dictionary for Regulatory Activities
mg	Milligram(s)
NCI	National Cancer Institute
NCS	Not Clinically Significant
PS	Pharmacokinetic Set
PT	Preferred Term
RNA	Ribonucleic Acid
RP2D	Recommended Phase II Dose
SAE	Serious Adverse Event
SAP	Statistical Analysis Plan
SD	Standard Deviation
SE	Standard Error
SOC	System Organ Class
SS	Safety Set
TEAE	Treatment-Emergent Adverse Event
TIL	Tumor-infiltrating Lymphocytes
TLFs	Tables, Listings, and Figures
TURBT	Transurethral Resection of Bladder Tumor
WHO	World Health Organization

## 1. INTRODUCTION

This document outlines the statistical methods to be implemented during the analyses of data collected within the scope of CicloMed LLC Protocol CPX-POM-002 [A Window of Opportunity Study to Characterize the Safety, Dose Tolerance, Pharmacokinetics, and Pharmacodynamics of CPX-POM in Patients with Newly Diagnosed or Recurrent Bladder Tumors]. The purpose of this plan is to provide specific guidelines from which the statistical analyses will proceed. Any deviations from this plan will be documented in the clinical study report (CSR).

## 2. STUDY OBJECTIVES

The primary purpose of this study is to evaluate safety and dose tolerance as well as investigate the mechanisms of action of CPX-POM in patients with newly diagnosed or recurrent, untreated or intravesical treatment completed >6 months before the current diagnosis, resectable bladder tumors, after administration of the recommended phase 2 dose (RP2D) to the target patient population. The patient population selected will have pre-dose tumor samples obtained by in-office cystoscopy available and will be scheduled for transurethral resection of a bladder tumor (TURBT), and therefore will not need to undergo additional, study-specific, invasive procedures.

### 2.1 Primary Objective

The primary objective of the study is to characterize the safety and dose tolerance of CPX-POM administered as 900 mg/m^2 IV by 20-minute IV infusion once daily for 5 days to patients with newly diagnosed or recurrent bladder tumors who will be scheduled to undergo TURBT.

### 2.2 Secondary Objectives

The secondary objectives of the study are:

- To determine the number of patients with treatment-related AEs
- To elucidate mechanisms of CPX-POM action on bladder tumor tissues employing an unbiased approach, using ribonucleic acid sequencing (whole transcriptome shotgun sequencing, RNA-seq) and chromatin immunoprecipitation-DNA sequencing (ChIP-seq)
- To determine the change in bladder tumor tissue cell proliferation, Notch and Wnt cell signaling pathways, as well as bladder tumor tissue CD8+ tumor-infiltrating lymphocytes (TIL) via immunohistochemistry
- To determine bladder tumor tissue-to-plasma and tissue-to-urine CPX concentration ratios

### 2.2 Exploratory Objective

The exploratory objective of the study is to determine urine  $\beta$ -glucuronidase activity.

### **3. STUDY DESIGN AND PLAN**

This will be an open-label study to determine the safety, dose tolerance, pharmacokinetics, and pharmacodynamics of CPX-POM in patients with newly diagnosed or recurrent, untreated or intravesical treatment completed >6 months before the current diagnosis, resectable tumors. Approximately 12 patients will be enrolled and treated with 900 mg/m^2 CPX-POM administered IV over 20 minutes once per day for 5 days followed by TURBT on Day 5 after the fifth dose. TURBT will be performed 2 to 6 hours following drug administration on Day 5.

Pretreatment bladder tumor tissues will be obtained at the time of in-office cystoscopy by cold cup biopsy within 4 weeks of TURBT. Posttreatment bladder tumor tissues will be obtained at TURBT. Bladder tumor tissues will undergo pathological evaluation at each site.

Prior to administration of the first CPX-POM dose on Day 1, pre-dose blood (plasma) and urine (clean catch) samples will be collected. At the time of TURBT on Day 5, one 3-mL blood (plasma) sample and a urine specimen will be collected for measurement of CPX-POM concentrations. The full schedule of assessments can be found in Table 1 of the protocol.

Patients will be followed for at least 30 days after the last dose of CPX-POM for safety.

### **4. DETERMINATION OF SAMPLE SIZE**

There were no formal sample size calculations conducted for this study as there are no formal statistical analyses planned. The estimated number of patients for this study is 12.

### **5. GENERAL ANALYSIS CONSIDERATIONS**

The statistical analyses will be reported using summary tables, listings, and figures (TLFs). The International Conference on Harmonisation (ICH) numbering convention will be used for all TLFs. Continuous variables will be summarized with sample size (n), mean, standard deviation (SD), median, interquartile range (IQR), minimums, and maximums. Other summaries (e.g., quartiles, 5%, 95% intervals, CV or %CV) may be used as appropriate. Mean, median, and IQR values will be formatted to one more decimal place than the measured value. SD will be formatted to two more decimal places than the measured value. Minimum and Maximum values will be presented to the same number of decimal places as the measured value. Categorical variables will be summarized by counts and by percentage of patients in corresponding categories.

All analyses and tabulations will be performed using SAS® Version 9.4 or higher. Tables, listings, and figures will be provided in PDF format.

#### **5.1 Missing or incomplete dates**

The most conservative approach will be systematically considered. If the AE onset date is missing / incomplete, it is assumed to have occurred during the study treatment phase (i.e.,

considered a TEAE) except if the partial onset date or other data such as the stop date, indicates differently. Similarly, a medication with partial start and stop dates could be considered as both a prior and concomitant treatment.

The following algorithms will be applied to missing and incomplete start and stop dates:

### **Start Dates**

- If the day portion of the start date is missing, then the start date will be estimated to be equal to the date of first dose of study drug, provided the start month and year are the same as the first dose of study drug and the stop date is either after the first dose of study drug or completely missing. Otherwise, the missing day portion will be estimated as '01'.
- If both the day and month portions of the start date are missing, then the start date will be estimated to be equal to the date of first dose of study drug, provided the start year is the same as the first dose of study drug and the stop date is either after the first dose of study drug or completely missing. Otherwise, the event will be assumed to start on the first day of the given year (e.g., ??-??-2021 is estimated as 01-JAN-2021).
- If the start date is completely missing and the stop date is either after the dose of study drug or completely missing, the start date will be estimated to be the day of study drug dosing. Otherwise, the start date will be estimated to be the first day of the same year as the stop date. All other non-AE and non-concomitant medication day calculations where only partial dates are available will be handled as follows: the first day of the month will be used in the calculations if the day part of a start date is missing while January 1 will be employed if both the month and day parts of a start date are missing.

### **Stop Dates**

- If only the day of resolution is unknown, the day will be assumed to be the last of the month (e.g., ??-JAN-2021 will be treated as 31-JAN-2021).
- If both the day and month of resolution are unknown, the event will be assumed to have ceased on the last known date on the study or the last day of the year (e.g., ??-??-2021 will be treated as 31-DEC-2021), whichever occurs earlier.
- If the stop date is completely missing or the event is continuing, the event will be assumed to be after first dose of study drug and will be imputed using the last known date on the study.

## **6. ANALYSIS SETS**

The following analysis sets will be used:

- Safety Set (SS) will consist of all patients who receive at least 1 dose of study drug. All safety and pharmacodynamic (PD) data will be analyzed using the safety set.
- Pharmacokinetic Set (PS) will consist of all patients for whom a tissue, plasma, and/or urine sample is obtained and analyzed for determination of plasma drug and metabolites concentration.

## 7. STUDY POPULATION

### 7.1 Patient Disposition

Patient disposition information will be summarized for all patients by treatment group (only 900 mg/m^2 CPX-POM). Summaries will include: the number of patients screened, the number of patients in each analysis set, the number of patients completing the study, the number of patients completing 5 days of dosing with CPX-POM and who undergo TURBT from which tissue, blood, and urine samples were collected, the number of patients who completed the Day 35 Follow-up Visit, the number of patients who died and the primary cause of death, the number of patients who had an autopsy, and the primary reason for discontinuation.

### 7.2 Protocol Deviations

Major protocol deviations that could potentially affect the efficacy or safety conclusions of the study will be identified prior to database lock.

Major protocol deviations will be summarized by deviation category and listed.

### 7.3 Demographics and Baseline Characteristics

Demographics including age, sex at birth, ethnicity, race and childbearing potential will be listed and summarized. Descriptive statistics will be presented for age. Frequency counts and percentages will be presented for sex, ethnicity, race, ECOG status and childbearing potential.

Baseline characteristics of height (measured at screening), weight (measured at Visit 1), BSA, and whether bladder tumor is newly diagnosed or recurrent will be summarized with descriptive statistics. BSA will be calculated by the site personnel using the Dubois method using screening height and baseline weight measurements.

Medical history will be mapped to preferred terms and system organ classes using the Medical Dictionary for Regulatory Activities (MedDRA) (version 23.1). Overall summaries will be provided by system organ class and preferred terms ordered by descending incidence of system organ class and preferred term within each system organ class. Medical history will also be listed.

### 7.4 Prior and Concomitant Medications

Prior and concomitant medication verbatim terms will be mapped to Anatomical Therapeutic Chemical (ATC) class and Preferred Names using the World Health Organization (WHO) Drug Dictionary Enhanced (version B3/September 2020).

Concomitant medications are defined as medications that started on or after the treatment start date or were ongoing at the date of treatment start. Prior medications are defined as medications that started and stopped prior to the date of treatment start. Medications taken within 30 days

before baseline (Study Visit 2) must be recorded as a prior medication. Prior and concomitant medications will be listed.

## **8. EFFECTIVENESS ANALYSES**

The primary objective of this study is to characterize the safety and dose tolerance of CPX-POM, there are no planned efficacy analyses. Pharmacokinetic and pharmacodynamic analyses of bladder tumor tissue, plasma and urine samples will be reported separately.

## **9. SAFETY ANALYSES**

All safety analyses will be based on the SS population. Data will be presented using descriptive statistics and no formal hypothesis testing will be implemented.

### **9.1 Baseline Values**

Baseline is be defined as the measurement taken at baseline safety assessment Visit #2 (Study Day 1). If that measurement is not available, baseline is defined as the last non-missing measurement recorded prior to CPX-POM administration.

### **9.2 Handling of Dropouts or Missing Data**

No imputations will be made for missing values. Summaries will be based on observed data only.

### **9.3 Extent of Exposure**

CPX-POM exposure will be summarized by visit and overall. Descriptive statistics for study drug administration will be presented for total dose administered and volume infused. Frequency counts and percentages will be presented for number of patients administered CPX-POM, number of infusions interrupted and the reason for interruption. CPX-POM adiminstration data will also be listed.

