6.1.2. Packaging and Labeling

CPX-POM will be packaged in plastic, 10-mL vials containing CPX-POM 50 mg/mL solution. Vials will be labeled according to applicable regulatory requirements.

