6.1.4. Dosage and Administration

At baseline, the body surface area (BSA) will be calculated by the Dubois method using Screening height and baseline weight measurements. The baseline BSA is to be used to determine the patient's study drug dose.

$$\text{Dubois Formula: } \text{BSA} = 0.007184 \times W^{0.425} \times H^{0.725}$$

CPX-POM will be administered as an IV infusion once daily on Days 1-5 of the study. CPX-POM will be added to a 100-mL piggyback bag of 0.9% sodium chloride solution and infused over a 20-minute period. The dose administered will be 900 mg/m².

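### SAP 9.3 summarises exposure to a 900 mg/m² dose only as total dose and volume, so body size is mixed with delivery and reduced or partial doses are not shown directly

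*SAP*

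**What the plan says.** Protocol 6.1.4 sets the regimen: "CPX-POM will be administered as an IV infusion once daily on Days 1-5 of the study", "The dose administered will be 900 mg/m²", and "The baseline BSA is to be used to determine the patient's study drug dose". The primary objective, in both documents, is the safety and dose tolerance of that regimen.

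SAP 9.3 plans four things:

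- Level of summary: "CPX-POM exposure will be summarized by visit and overall".
- Statistics: "Descriptive statistics for study drug administration will be presented for total dose administered and volume infused". The section gives no unit for dose and does not say which volume is meant.
- Counts: "Frequency counts and percentages will be presented for number of patients administered CPX-POM, number of infusions interrupted and the reason for interruption".
- A listing: "CPX-POM adiminstration data will also be listed".

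Three other SAP sections bear on exposure. Section 7.1 counts patients who complete five days of dosing and also have TURBT with tissue, blood and urine collected. Section 7.3 summarises BSA as a baseline characteristic. Section 9.4 tabulates TEAEs leading to study discontinuation, but none leading to dose reduction or interruption.

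Protocol 6.1.5 discourages dose modification. It allows one to be discussed with the Medical Monitor when a patient has an SAE that the investigator thinks a modification may mitigate.

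Neither document plans dose received in mg/m², percent of planned dose, or a count of patients with reduced doses.

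**The concern.** When a dose is assigned per square metre, two patients who receive the whole regimen have different totals in mg simply because they differ in size. A table of total mg therefore describes the body sizes of the sample as well as delivery of the drug. Drug volume has the same weakness, because it is proportional to mg.

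The study asks whether 900 mg/m² daily for five days is tolerated, so the share of the regimen that each patient received is part of the answer. A reduced or unfinished infusion is the exposure finding closest to that question. In the planned tables such a patient still counts as dosed, and the shortfall is absorbed into a mean and SD whose spread comes largely from BSA.

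**Working it through.** The plan states no exposure figure to reproduce. Inputs from the documents are 900 mg/m² per day, 5 doses, the Dubois BSA formula, a 100-mL saline bag per infusion (Protocol 6.1.4), a 50 mg/mL solution (Protocol 6.1.2) and about 12 patients. The documents give no BSA distribution, so every BSA, weight and height below is an assumption.

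**1. Total dose in mg.** Total = doses given × 900 × BSA.

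- BSA 1.6 m², five doses: 5 × 900 × 1.6 = 7200 mg.
- BSA 2.4 m², four doses: 4 × 900 × 2.4 = 8640 mg.
- The second patient has 8640/7200 = 1.20 times the mg, but 3600 mg/m² against 4500 mg/m².

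Four doses exceed five in mg when the BSA ratio is above 5/4 = 1.25. Three doses exceed five when it is above 5/3 = 1.67.

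**2. Spread with perfect delivery.** The Dubois formula gives 1.467 m² for 50 kg and 155 cm, and 2.448 m² for 120 kg and 188 cm. Five full doses are then 6601 mg and 11015 mg, a 1.67-fold difference due to size alone. With mean BSA 1.90 to 1.95 and SD 0.15 to 0.25, the coefficient of variation of a fully dosed total is 0.15/1.90 = 8% to 0.25/1.95 = 13%. By comparison, one missed dose among 12 × 5 = 60 moves the mean total by about 1/60 = 1.7%, taking equal BSAs.

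**3. How often totals overlap.** For independent normal BSAs with mean m and SD s, the probability that a four-dose total exceeds a five-dose total is Φ(−m / (s√(4² + 5²))).

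- m = 1.90, s = 0.15: Φ(−1.98) = 2%.
- m = 1.90, s = 0.20: Φ(−1.48) = 7%.
- m = 1.95, s = 0.25: Φ(−1.22) = 11%.

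Take a purely illustrative 25% reduction on Days 3 to 5, which leaves 2 + 3 × 0.75 = 4.25 dose equivalents. The same formula with 4.25 in place of 4, and 0.75m in place of m, gives 7% to 19%.

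**4. By-visit dose.** An illustrative dose at 75% for BSA 2.2 m² is 0.75 × 900 × 2.2 = 1485 mg. A full dose for BSA 1.6 m² is 1440 mg. With 12 patients of equal BSA, one patient at 75% lowers that visit's mean by 0.25/12 = 2.1%, and the number dosed stays at 12.

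**5. Volume.** Drug volume is 900/50 = 18 mL per m² per day, so it behaves exactly like mg. If the bag is counted, volume per infusion is 100 + 18 × BSA:

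- Four infusions at 2.448 m²: about 576 mL.
- Five infusions at 1.467 m²: about 632 mL. Over this range a missed dose does not overtake a full course.
- At 1.81 m², a 25% reduction changes one infusion by 0.25 × 32.6 = about 8 mL out of 133 mL, so a reduced dose is barely visible.

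**6. Normalised measures.** In mg/m², every fully dosed patient has 4500 (100%) and every patient missing one dose has 3600 (80%), whatever their size.

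**The case against.** The strongest reply is that SAP 9.3 should be read as a whole. A missed dose lowers the by-visit count of patients dosed. Interrupted infusions and their reasons are tabulated. With about 12 patients and a listing, anyone can read the data patient by patient and rebuild mg/m² from dose and BSA. All of this stands for missed doses. The count in SAP 7.1 helps less, because a fully dosed patient who lacks one sample drops out of it.

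The by-visit layout also helps. Planned mg rests on baseline BSA and so is constant over the five days. If the same patients are dosed at two visits, body size cancels and a shift in the mean points to a changed or incomplete dose. This is correct but indirect. The shift is small (step 4), a change in who is dosed blurs it, offsetting changes can hide it, and it does not say how many patients were affected.

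Reductions may also be uncommon: treatment lasts five days and Protocol 6.1.5 discourages them. Protocol 2.1 reports only Grade 1 related AEs at this dose, but in six patients and with a 10-minute infusion, which cannot exclude them.

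Three stronger readings are tempting, and the documents do not support them:

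- That the plan cannot show how much of the regimen was delivered. The counts, by-visit summaries and listing show part of it.
- That the tables rank an under-dosed patient above a fully dosed one. Descriptive statistics rank nobody. The overlap in steps 1 and 3 shows only that total mg is a poor measure of delivery.
- That the SAP specifies raw mg and that volume always misleads. No unit is given, and the volume result depends on whether the bag is counted.

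**Conclusion.** The point holds as a gap in reporting. SAP 9.3 plans no exposure measure on the scale on which the dose is assigned, and no planned summary directly shows reduced or partial doses, although dose tolerance is the primary objective.

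The size rests on reading total dose as mg and on assumed BSAs. On that basis, fully dosed totals can differ 1.67-fold through body size alone, and one missed dose is masked in mg when the BSA ratio exceeds 1.25. The 1.6 and 2.4 m² pair is a wide contrast, not a typical one. For randomly paired patients the overlap is 2% to 11%.

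No hypothesis test is planned (SAP 4 and 9), so no inference is damaged. The effect is on how well the report describes delivery of the regimen. The change should be made because it is better and almost free, not because the present plan invalidates the study.

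**What to change.** In SAP 9.3, state the unit of total dose and whether volume infused includes the diluent. Add to the existing summaries:

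1. Dose received in mg/m², by visit and cumulatively: actual mg divided by the baseline BSA used for dosing. Take the BSA recorded for dosing, because SAP 7.3 summarises Visit 1 weight, whereas footnote 14 to Protocol Table 1 bases BSA on Visit 2 weight.
2. Percent of planned dose: actual mg / (900 × baseline BSA × 5).
3. Number of doses received per patient (0 to 5), and number and percentage of patients with any missed, reduced or incomplete dose.

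The total dose and volume summaries can stay. BSA, dose and volume are already collected, so the cost is SAP wording and a few derived variables. No assessment is added, and the sample size and study conduct do not change.
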